9.1 Analysis Populations

9.1.1 Safety Population

The safety population is defined as all subjects who receive at least one dose of the study treatment.

9.1.2 Pharmacokinetic Population

The PK population will include all subjects data from the safety population who complete at least two periods, including Treatment B, and for whom the PK profile can be adequately characterized.

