5.4 Subject Withdrawal and Replacement

Subjects will be advised that they are free to withdraw from the study at any time. Over the course of the study, the Sponsor and the Investigator or designee may withdraw any subject from the study for one of the reasons described below; subject withdrawal will be done in accordance with the clinical site's SOP:

- Safety reason;
- Non-compliance with protocol requirements;
- Significant protocol deviation;
- Positive pregnancy test, drug screen, or alcohol breath test.

Subjects who experience vomiting within 10 hours after study treatment administration will be removed from that period of the study. Their continued participation in the study will be evaluated by the Investigator and PK Scientists prior to the next study treatment administration.

Subjects who experience vomiting after this time will be assessed for their continued participation in the study by the Investigator.

Subjects excluded from dosing in one period as per criteria listed above, may be invited to participate in subsequent periods of the study if deemed appropriate by the Investigator and appropriate from a statistical standpoint (i.e., would permit adequate statistical comparison). However, subjects with positive pregnancy test, drug screen, or alcohol breath test will be definitively withdrawn from the study.

Subjects who withdraw prior to the first dosing may be replaced with a standby subject. Subjects who withdraw or are withdrawn from the study after the first dosing will not be replaced.

Subjects who withdraw or are withdrawn will be asked to remain at the clinic until the Investigator or designee agrees that the subject is fine and can be discharged. As soon as subject withdrawal is confirmed, blood sampling will be stopped. A PK blood sample may be collected at the time of withdrawal if deemed required by the Investigator. EOS/early termination (ET) procedures will be performed at the time of withdrawal from the study or as soon as possible thereafter.

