6.6 Administration of Food and Fluid

For Treatment A:

Subjects will fast from at least 10 hours prior to study treatment administration until at least 4 hours post-dose.

For Treatment B, C, and D:

After an overnight fast of at least 10 hours, subjects will consume a high-fat, high-calorie breakfast starting 30 minutes prior to study treatment administration.

Table 4. High-Fat, High-Calorie Breakfast

	Calories (kcal)	Total Fat (g)	Carbohydrates (g)	Protein (g)
2 eggs	140	10	0	12
10 g of butter for cooking eggs	70	8	0	0
2 slices of whole wheat toast (approximately 64 g)	160	2	31	7
10 g of butter for toast	70	8	0	0

3 triangle pieces of hash brown potatoes (approximately 130 g)	218	14	23	2
250 mL of whole milk	160	8	12	8
3 strips of chicken bacon (approximately 63 g)	105	7	0	9
Total weight (g)		57	66	38
Total calories (kcal)	923	514	262	152
Relative caloric content		56%	28%	16%

Note: Due to supply chain issues, some ingredients may not be available therefore, the content of the high-fat, high-calorie breakfast is subject to change. Any change will be notified to the Sponsor and ensured that the total caloric content and breakdown between fat, carbohydrate, and protein is maintained according to FDA requirements: high-fat (approximately 50 percent of total caloric content of the meal) and high-calorie (approximately 800 to 1000 calories). The meal should derive approximately 150, 250, and 500-600 calories from protein, carbohydrate, and fat, respectively.⁷

Subjects who do not consume the entire meal in the required time will be dismissed from that period of the study prior to study treatment administration. Their continued participation in the remainder of the study will be determined by the Investigator or designate.

Subjects will fast for at least 4 hours post-dose.

For all Treatments:

Standardized meals will be provided throughout confinement (e.g., at 4 hours for lunch, 9 hours for dinner and 13.5 hours for snacks). The meals will be identical for all periods.

Water will be restricted from one hour prior to study treatment administration until one hour post-dose (except the water administered with the study treatment in Treatment C and D). Access to water will otherwise be freely available to subjects.

7. Study Restrictions

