9.1.3 Pharmacokinetic Statistical Population

The PK statistical population will include all subject's data from the PK population who complete at least two periods, where a statistical comparison can be made for at least one PK parameter and who have not experienced any protocol deviations or other circumstances to exclude the subject from the PK statistical analysis.

Individual period data will be excluded if a baseline-corrected pre-dose concentration (at time 0-hour) greater than 5% of the corresponding C_{max} is observed for a subject.

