9.2 Pharmacokinetic Parameters

The actual post-dose sample collection times will be used in the PK analysis.

The following PK parameters and observations will be calculated based on data from the PK population
[REDACTED]
later) for ba

- AUC_{0-t} : Area under the concentration-time curve from time zero until the last observed concentration, as calculated by the linear up/log down variant of the trapezoidal method.

- $AUC_{0-\infty}$: Area under the concentration-time curve from time zero to infinity (extrapolated)
- Residual area: Percentage of $AUC_{0-\infty}$ due to extrapolation from the time of the last observed concentration to infinity, calculated as $[1 - (AUC_{0-t}/AUC_{0-\infty})] \times 100$
- C_{\max} : Maximal observed concentration
- T_{\max} : Time when the maximal concentration is observed
- T_{lag} : Time of observation prior to the first observation with a measurable (non-zero) concentration.
- $T_{1/2 \text{ el}}$: Terminal elimination half-life
- K_{el} : Terminal elimination rate constant
- Cl/F : Apparent clearance
- V_z/F : Apparent volume of distribution
- R^2 : Coefficient of determination obtained from regression analysis

Additional PK parameters may be calculated. K_{el} , $T_{1/2 \text{ el}}$, and $AUC_{0-\infty}$ parameters will not be estimated for concentration-time profiles where the terminal linear phase is not clearly defined.

Sapropterin is an endogenous compound and therefore, should be analyzed both with and without baseline correction. Pharmacokinetic parameters will be calculated based on uncorrected plasma concentrations and baseline-corrected plasma concentrations, as appropriate. Baseline corrected for sapropterin will be performed by calculating the mean plasma pre-dose levels for each subject within each period of the study using the measured concentrations at the -1, -0.5, and the 0-hour time points. The mean of these pre-dose values will be the *baseline* for that period for that subject. The baseline value will be subtracted from all subsequent measured concentrations (including 0-hour) for the same subject within the same period. Negative baseline adjusted levels will be set to zero before the PK analysis. No adjustment of the pre-dose or post-dose concentrations will be performed for the baseline uncorrected data.

IRB Reviewed - June 12, 2024

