9.3 Pharmacokinetic Statistical Analysis

Statistical analysis described in this section will be based on the PK statistical population.

Individual and mean plasma concentration versus time curves will be presented for both linear and semi-log scales.

Descriptive statistics for the PK parameters of baseline-corrected and uncorrected sapropterin will be calculated. Descriptive statistics will include number of observations, arithmetic mean, standard deviation, geometric mean (where applicable), coefficient of variation (CV), median, minimum, and maximum.

Statistical analysis will be performed on quality assured data, with unbalanced sequences if necessary, from subjects in the statistical dataset. The PROC MIXED procedure from SAS® (version 9.4 or later) will be used.

ANOVA will be performed on log-transformed AUC_{0-t} , $AUC_{0-\infty}$, and C_{max} parameters at the alpha level of 0.05 on uncorrelated data, the statistical model will include sequence, treatment, period, and subject(sequence) as a random effect.

ANCOVA (Analysis of Co-Variance) on log-transformed AUC_{0-t} , $AUC_{0-\infty}$, and C_{max} parameters at the alpha level of 0.05 will be applied for baseline corrected analysis, using the actual total dose included in the ANOVA statistical model as a covariate, the statistical model will include sequence, treatment, period, and actual total dose as fixed effects and subject(sequence) as a random effect.

In case the study is dosed in groups, considering the study conduct will occur at the same clinical site, assignment to groups is random, and the dosing of the groups will occur within a relatively short timeframe, it is not anticipated that dosing in groups will impact the study results. As such, the group effect will not be considered in the statistical model.

Using the same statistical model, the least-squares-means, the differences between the treatments least-squares-means, and the corresponding standard errors of these differences will be estimated for log-transformed AUC_{0-t} , $AUC_{0-\infty}$, and C_{max} parameters. Based on these statistics, the ratios of the geometric means for treatments and the corresponding 90% confidence interval will be calculated for the following comparisons:

- Treatment A versus Treatment D
- Treatment B versus Treatment D
- Treatment C versus Treatment D
- Treatment B versus Treatment C
- Treatment A versus Treatment C
- Treatment B versus Treatment A

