These contrasts will be estimated separately using only the data from the treatments involved in the comparison.

Treatment differences in T_{max} will be evaluated by a nonparametric approach (Wilcoxon signed rank test) on the untransformed values.

These statistics will be used to evaluate the effect of food on the test formulation and the performance of the test formulation with and without water.

Additional PK statistical analysis may be performed. For example, an analysis with potency corrected data (to adjust the ratio and 90% CI for the comparison between Test and Reference B/D), in the event that the measured study treatment content of the lots of the Test and Reference products would differ by more than 5%.

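### Making Treatment B compulsory for the PK population discards valid A/D, C/D and A/C pairs, although those contrasts use no Treatment B data

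*Combined protocol and SAP*

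**What the plan says.** Section 9.1.2 sets the entry rule: "The PK population will include all subjects data from the safety population who complete at least two periods, including Treatment B", with an adequately characterised profile. Section 9.2 adds that "The following PK parameters and observations will be calculated based on data from the PK population". Section 9.1.3 builds the next population from "data from the PK population who complete at least two periods, where a statistical comparison can be made for at least one PK parameter", and 9.3 opens with "Statistical analysis described in this section will be based on the PK statistical population". The B requirement thus carries through from parameter calculation to every contrast.

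Section 9.3 lists six contrasts: A/D, B/D, C/D, B/C, A/C and B/A. It then says: "These contrasts will be estimated separately using only the data from the treatments involved in the comparison".

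The plan foresees subjects missing a single period. On the fed breakfast, 6.6 says: "Subjects who do not consume the entire meal in the required time will be dismissed from that period of the study". On vomiting, 5.4 says: "Subjects who experience vomiting within 10 hours after study treatment administration will be removed from that period of the study". Subjects excluded from one period "may be invited to participate in subsequent periods of the study if deemed appropriate by the Investigator", provided this also makes statistical sense. Subjects lost after first dosing are not replaced (5.4), and 16 are planned (5.1).

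**The concern.** Three of the six contrasts do not involve B, and the plan estimates them without B data. Requiring B therefore adds nothing to them and removes subjects who have both treatments of the pair. No visible text exempts these contrasts or explains the condition.

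One of the three, C/D, is the Test/Reference comparison in which both arms are fed and the total volume taken is 240 mL (suspension plus water for C; 120 mL plus two 60 mL rinses for D). The study's output is a set of ratios with 90% confidence intervals from a small sample, so precision is what it has to offer. Under dropout the rule also acts unevenly across sequences, because B comes late in DCAB (Period 4) and ADBC (Period 3) but early in BACD and CBDA.

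Two lesser points follow. Section 5.4.1 says data from discontinued subjects will be used where applicable, which sits uneasily with the rule. Section 9.1.4 ties assay to a PK dataset that is never defined, and this can be read as leaving these subjects' samples unassayed.

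**Working it through.** **1. Which pairs the rule removes.** The sequences are those of Table 3. The plan gives no figure to reproduce here.

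| Situation | Complete pairs | Pairs kept under 9.1.2 |
|---|---|---|
| Misses only A | B/D, C/D, B/C | all three |
| Misses only C | A/D, B/D, B/A | all three |
| Misses only D | B/C, A/C, B/A | all three |
| Misses only B (any sequence) | A/D, C/D, A/C | none |
| DCAB leaves after Period 2 | C/D | none |
| ADBC leaves after Period 2 | A/D | none |
| BACD leaves after Period 2 | B/A | B/A |
| CBDA leaves after Period 2 | B/C | B/C |
| DCAB leaves after Period 3 | A/D, C/D, A/C | none |
| ADBC, BACD or CBDA leaves after Period 3 | three each | all three |

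**2. Effect on precision.** Each contrast is fitted on its two treatments with subject, period and treatment effects. Sequence is a fixed effect and every contributing subject has both treatments, so the treatment estimate is purely within-subject. With v the variance of the estimated log ratio in units of σ_w²:

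90% CI half-width = t(0.95, df) × √v × σ_w, where σ_w = √ln(1 + CV²).

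The baseline is 4 subjects in each of the four sequences.

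*A/D and C/D*

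| Subjects lost | v | df | Half-width relative to 16 subjects |
|---|---|---|---|
| none | 0.1250 | 12 | 1 |
| any one | 0.1354 | 11 | 1.049 |
| two DCAB | 0.1563 | 10 | 1.137 |
| two DCAB and one ADBC | 0.1667 | 9 | 1.188 |
| three DCAB | 0.2188 | 9 | 1.361 |
| all four DCAB | – | – | not estimable (treatment aliased with period) |

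For one subject lost: (1.7959 × √0.1354) / (1.7823 × √0.1250) = 0.661 / 0.630 = 1.049. For C/D, the row with one ADBC subject arises only if that subject misses B alone.

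*A/C*

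| DCAB subjects lost | v | df | Half-width relative to 16 subjects |
|---|---|---|---|
| none | 0.1250 | 13 | 1 |
| one | 0.1346 | 12 | 1.044 |
| two | 0.1500 | 11 | 1.111 |
| three | 0.1786 | 10 | 1.223 |
| four | 0.2500 | 9 | 1.464 |

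For A/D and A/C, the DCAB rows can be blamed on the rule only if those subjects completed Period 3. A DCAB subject who leaves after Period 2 has no A, so the pair is missing anyway.

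**3. On the ratio scale.** The documents give no within-subject CV, so 20%, 30% and 40% are assumed (σ_w = 0.198, 0.294, 0.385). The 90% CI for A/D or C/D around a ratio of 1 is:

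| CV | 16 subjects | One lost | Three DCAB lost |
|---|---|---|---|
| 20% | 88.3–113.3% | 87.7–114.0% | 84.4–118.5% |
| 30% | 83.1–120.3% | 82.4–121.4% | 77.7–128.6% |
| 40% | 78.4–127.5% | 77.5–129.0% | 71.9–139.1% |

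**4. How likely it is.** The documents give no dropout rate either. Suppose each subject independently misses B with probability p = 5%, 10% or 20%.

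- Expected number affected, 16p: 0.8, 1.6 or 3.2.
- Chance of at least one, 1 − (1 − p)^16: 56%, 81% or 97%.
- Chance that at least three of the four DCAB subjects are affected, 4p³(1 − p) + p⁴: about 0.05%, 0.4% or 2.7%.

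**The case against.** The strongest reply is that little is at stake. This is a pilot study with no formal hypothesis test, and the visible text sets no acceptance limits for these contrasts. One lost subject widens an interval by about 5%, and the large figures need most of one four-person sequence to be lost. That is fair: one subject is the main case, and the multi-DCAB rows are extremes. It limits the size of the problem but gives no reason to keep the rule.

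A second reply is that B may be the deliberate anchor. The objectives and the text following the sample size are redacted, and 9.3 names B/D for potency correction. But any subject contributing to B/D, B/C or B/A already has B and one other period. With the two-period minimum kept, removing the B condition leaves all three of those datasets unchanged, so a B-centred purpose does not need it.

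Some supporting points are softer. Section 5.4.1 is qualified and can be read as deferring to the population definitions, so it is a tension and not a contradiction. Section 9.1.4 mentions subjects who vomit within the removal criteria among those whose samples are assayed, so the reading that samples go unassayed is uncertain. Return after a missed period depends on judgement by the investigator and on statistical grounds. A subject with A, C and D does, however, permit comparisons, which is the statistical condition 5.4 sets.

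**Conclusion.** The concern holds. Followed as written, the plan drops usable A/D, C/D and A/C pairs from subjects who lack B, with no benefit to any contrast. The realistic cost is about 5% on the log-scale interval for A/D or C/D, and about 4% for A/C, per affected subject at the first loss. The cost grows faster if losses cluster in DCAB, and it is zero if everyone completes B. The relative widths rest on four subjects per sequence and the two-treatment model. The intervals also rest on assumed CVs, and the likelihoods on assumed, independent rates of missing B. The loss is confined to PK, since these subjects stay in the safety population. It should be fixed before data are seen, because waiving the rule later would be a post hoc change of analysis population.

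**What to change.** - In 9.1.2, delete the Treatment B condition and keep the minimum of two completed periods.
- In 9.3, state that each contrast includes every subject in the PK statistical population with evaluable data for both of its treatments.
- In 9.1.4, define the PK dataset and say explicitly that samples from subjects without B will be assayed.
- Align 5.4.1 with the revised definitions.

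The cost is a wording change. If these samples would otherwise not have been assayed, add 20 per completed period, that is 40 to 60 already-drawn samples for each affected subject with two or three completed periods. No clinical procedure changes.

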9.1.3 Pharmacokinetic Statistical Population

The PK statistical population will include all subject's data from the PK population who complete at least two periods, where a statistical comparison can be made for at least one PK parameter and who have not experienced any protocol deviations or other circumstances to exclude the subject from the PK statistical analysis.

Individual period data will be excluded if a baseline-corrected pre-dose concentration (at time 0-hour) greater than 5% of the corresponding C_{max} is observed for a subject.

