8.8 Premature Termination of the Study

The study may be prematurely terminated by the Investigator following consultation with the Sponsor, by the Sponsor or by the regulatory authorities. Following a decision to discontinue the trial, the Investigator will promptly inform the active study subjects and the IEC responsible for this trial, stating the reasons for discontinuation of the study. It is the responsibility of the Sponsor (or representative) to report the premature termination of the study to the regulatory authority(ies), when required by the applicable regulatory requirement(s).

9. Statistical Analyses

For all PK analysis, all concentrations below the limit of quantification will be set to 0.

Samples with invalid concentration (due to bioanalytical or clinical issue) will be replaced by “0.00” when it occurs prior to dosing for PK parameters calculation. Otherwise, they will be set to missing for tabulation, graphical representation, and calculation purposes if it occurs after dosing.

The primary objective of this study is to evaluate the relative bioavailability of a new oral suspension formulation. Since this study is exploratory, no formal hypothesis testing is defined.

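### An invalid pre-dose sample of an endogenous analyte is set to zero; this can lower the baseline and, through the 5% rule, remove a sound period from both the corrected and uncorrected analyses (minor)

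*Combined protocol and SAP*

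**What the plan says.** The opening paragraphs of section 9 deal with invalid samples: "Samples with invalid concentration (due to bioanalytical or clinical issue) will be replaced by" 0.00 "when it occurs prior to dosing for PK parameters calculation". After dosing, invalid samples become missing instead.

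Section 9.2 forms the baseline for each subject and period "using the measured concentrations at the -1, -0.5, and the 0-hour time points". It continues: "The baseline value will be subtracted from all subsequent measured concentrations (including 0-hour) for the same subject within the same period". Then: "Negative baseline adjusted levels will be set to zero before the PK analysis". For the other version of the data: "No adjustment of the pre-dose or post-dose concentrations will be performed for the baseline uncorrected data".

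Section 9.1.3 applies a deletion rule: "Individual period data will be excluded if a baseline-corrected pre-dose concentration (at time 0-hour) greater than 5% of the corresponding" Cmax is observed. It gives neither the purpose of the rule nor which Cmax is meant. Section 9.3 opens with: "Statistical analysis described in this section will be based on the PK statistical population". Section 3 lists both the uncorrected and the baseline-corrected parameters as primary endpoints.

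**The concern.** Zero is a natural pre-dose value for a drug that is not otherwise in the body. Sapropterin is endogenous, so zero is not a plausible value for a lost or failed sample. If the zero enters the three-sample mean, the baseline is understated and every corrected concentration in that period is overstated. If the zero sits at -1 h or -0.5 h, an ordinary 0-hour value also appears to stand above its baseline, and the 5% rule may then delete a period in which nothing is wrong with the dose or the profile.

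The deletion reaches further than the correction that causes it. One population serves all of section 9.3, so the period also leaves the uncorrected analysis, where no baseline is subtracted. Section 9.3 estimates each contrast from the two treatments involved only. One lost Treatment A period therefore breaks one of at most 16 pairs in each of A/D, A/C and B/A.

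**Working it through.** **Inputs.**
- Endogenous level b: about 3-10 ng/mL (section 1.1); I use 3, 6 and 10.
- Cmax: 84.1 (42.2) intact/fasting and 105 (32.1) intact/fed (Table 2). I assume these are mean (SD), lognormal and not baseline-corrected, and that tablets stand in for the study products.
- AUC0-t: 474 and 635 ng.h/mL; mean half-lives 2.80-4.65 h (Table 2).
- Washout at least 7 days = 168 h (section 4); 24 h of sampling; 16 subjects.

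The 5% is a rule, so the plan has no derived figure to reproduce.

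**1. What the rule tests.** Corrected C0 = C0 - [C(-1) + C(-0.5) + C0]/3 = [2 x C0 - C(-1) - C(-0.5)]/3. Level pre-dose values give 0. Falling values give a negative number, which is set to 0. Only a rise before dosing can trigger the rule. After the washout, 168/4.65 = 36.1 half-lives have passed, leaving 2^-36.1 = 1.3e-11 of the drug.

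**2. One zero in the mean, the other two samples level at b.** Baseline = 2b/3, which is b/3 too low. Over 24 h, corrected AUC is too high by 24 x b/3 = 8b:

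| b (ng/mL) | Excess (ng.h/mL) | % of 474 | % of 635 |
|---|---|---|---|
| 3 | 24 | 5.1 | 3.8 |
| 6 | 48 | 10.1 | 7.6 |
| 10 | 80 | 16.9 | 12.6 |

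As a check, I applied the linear-up/log-down method to a one-compartment profile (Tmax 2.77 h, half-life 3.67 h, Cmax 84.1, AUC 737). It gives +25.7, +50.9 and +84.2 ng.h/mL, or 3.5, 6.9 and 11.4%. The percentages depend on the base AUC. On the 474 base, one such period in 16 shifts a treatment's geometric mean by ln(1.051)/16 = 0.3%, ln(1.101)/16 = 0.6% and ln(1.169)/16 = 1.0%.

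**3. When the rule then deletes the period.** With the zero at -1 h or -0.5 h, corrected C0 = b - 2b/3 = b/3.
- If uncorrected Cmax is meant: b/3 > 0.05 x Cmax, so Cmax < 6.67b.
- If corrected Cmax is meant: b/3 > 0.05 x (Cmax - 2b/3), so observed Cmax < 7.33b.
- If the 0-hour sample is the zero, corrected C0 is negative, is set to 0, and the rule cannot fire.

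Lognormal parameters: sigma^2 = ln[1 + (SD/mean)^2] and mu = ln(mean) - sigma^2/2. Fasting: sigma 0.474, mu 4.320. Fed: sigma 0.299, mu 4.609. Share of periods below the cut-off, given one such zero:

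| b | Cut-offs (ng/mL) | Fasting-type | Fed |
|---|---|---|---|
| 3 | 20-22 | 0.3-0.5% | 0% |
| 6 | 40-44 | 9.2-12.9% | 0.1-0.3% |
| 10 | 66.7-73.3 | 40.0-47.9% | 8.5-14.7% |

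If Table 2 is already baseline-corrected, the cut-offs on its scale fall by b, to 5.67b and 6.33b. The fasting shares become 0.1-0.2%, 4.7-7.5% and 28-36%, and the fed shares 0%, under 0.1% and 2.8-6.2%.

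**4. Expected loss.** The documents give no invalid-sample rate. Assume p = 1-5% per sample, with two samples at risk per period: loss = 16 x 2 x p x share. For Treatment A this is under 0.01 period at b = 3, 0.03-0.21 at b = 6 and 0.13-0.77 at b = 10. For each fed treatment it is 0, 0.0003-0.005 and 0.03-0.23.

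**5. What the rule can usefully catch.** An isolated 0-hour error d leaves a corrected value of 2d/3, so the rule fires when d > 7.5% of Cmax: 0.075 x 84.1 = 6.3 ng/mL. Such an error raises the baseline by d/3 = 2.1, and corrected AUC is then about 24 x 2.1 = 50 ng.h/mL too low (about 60 on the profile in step 2).

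**The case against.** The best defence rests on the wording of 9.2. A substituted 0.00 is not a measured concentration, and the -1 h and -0.5 h samples enter no listed parameter except through the baseline. On that reading the substitution touches only the 0-hour point, where the rule cannot fire. This is a fair reading, but the plan does not state it. Section 9 orders the substitution explicitly for parameter calculation, and nothing exempts the baseline, so the two sections remain unreconciled.

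The objection on size largely stands. Three of the four treatments are fed, the large deletion shares need a high endogenous level, and the study is an exploratory pilot without formal hypothesis testing.

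Three stronger readings are tempting, and the documents do not support them.
- A reader might infer that the rule's blindness to flat or falling residual drug leaves carry-over undetected. The algebra is right, but after at least 36 mean half-lives there is nothing material to detect.
- A reader might take the 40-48% as a forecast of lost data. It is conditional on a zero-filled early sample and on b = 10.
- A reader might conclude that automatic deletion should go altogether. Step 5 shows that it can remove a period with a damaging 0-hour error, so keeping it in the corrected analysis is a defensible trade-off.

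**Conclusion.** The point holds as a minor one. Zero is the wrong substitute for an invalid pre-dose sample of this analyte, and the plan does not say whether it enters the baseline. If it does, a retained period has its corrected AUC overstated by roughly 3.5-17%, depending on b and on the base AUC. A period with low Cmax relative to b can be deleted for no reason of its own. The expected effect on the trial is small: less than one Treatment A period out of 16 even at an assumed 5% invalid rate with every subject at 10 ng/mL, and far less in fed periods.

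Separately, and whichever reading of the baseline is taken, deleting uncorrected data because of a value that exists only after correction has no stated justification. The shares rest on Table 2 tablet data, read as lognormal and uncorrected; the 8b bias and the cut-offs rest only on level pre-dose values.

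**What to change.** 1. In section 9, set an invalid pre-dose sample to missing and compute the baseline in 9.2 from the remaining valid pre-dose samples. If none remains, report no corrected parameters for that period. If the 0-hour sample is the missing one, also state the time-0 value for uncorrected AUC, for example the same mean. That choice moves AUC by only b x 0.333/2 = 0.5-1.7 ng.h/mL.
2. In 9.1.3, confine the baseline-corrected 5% exclusion to the baseline-corrected analysis, state that corrected Cmax is the comparator, and report that analysis with and without the excluded periods.

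The cost is wording and one extra set of tables, on samples already planned. A two-sample baseline has a standard error sqrt(3/2) = 1.22 times that of a three-sample one, or 22% larger. At b = 6 and an assumed within-hour CV of 20% (SD 1.2), that is 1.2/sqrt(2) = 0.85 against 1.2/sqrt(3) = 0.69 ng/mL, compared with a bias of b/3 = 2 ng/mL from the zero.
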